4.4.2 Data Collection and Follow-up for Withdrawn Subjects

Even though a subject has withdrawn from the study, it may be important to collect some follow-up data on such subjects throughout the protocol defined follow-up period. Such data is important to the integrity of the final study analysis since early withdrawal could be related to the safety profile of the study drug. If a subject withdraws consent to participate in the study, for subject safety reasons, attempts will be made to obtain permission to collect follow up information whenever possible.

5 Study Drug

5.1 Description

Iron sucrose solution supplied as Venofer® in a liquid form available in vials of 100 mg/5 mL and 200 mg/10 mL.

5.2 Treatment Regimen

One treatment dose will be administered during this study and will take place during the First Study Visit. The treatment dose will be 5 mg/kg of intravenous iron sucrose (maximum dose of 200 mg). Iron sucrose will be diluted to a concentration of 1 mg of elemental iron in 1 mL of NaCl 0.9% (maximum volume of 210 mL). The infusion will be infused at 3.5 mL/minute. A flush of 10 mL of NaCl 0.9% will be given after the infusion.

5.3 Method for Assigning Subjects to Treatment Groups

Subjects entering the study will be randomized through the clinical trials research pharmacy using a 1:1 randomization process. The Primary Investigator will be blinded to the randomization process. The randomization key will be readily available in the event of a medical emergency associated with the study intervention.

5.4 Preparation and Administration of Study Drug

The Clinical Research Unit's Research Pharmacy will obtain Venofer® supplied in vials of 100 mg/5 mL, from standard hospital supply at Mayo Clinic Hospital Rochester, MN. The preparation of the study drug will take place in the Clinical Research Unit Research Pharmacy and will include the dilution of the drug to the recommended concentration of 1 mg/mL. The drug will be maintained within recommended temperature ranges of 20°C to 25°C with excursions permitted to 15°C to 30°C[28]. Venofer® does have a brown color in concentrated form. To ensure adequate blinding of study team members, the IV solution bag and tubing will be wrapped by the Research Pharmacy to conceal color.

The study drug will have an accessory label reading "CAUTION: NEW DRUG LIMITED BY FEDERAL LAW TO INVESTIGATIONAL USE" as required by Federal Law. It will also have a finished product label from the Research Pharmacy. Below is a sample template:

IRB – Iron Sucrose/Placebo	Dose: 1 each
Sodium Chloride 0.9%	Dose: 100 mL
Route: IV	Frequency: Once

Rate: _____ mL/hour

Start Date/Time:

Comment: IRB# 12-009963; Iron Sucrose mg vs placebo

Clinical Research Pharmacy Director:

[name]., R.Ph. [name] Saint Mary's Hospital [name]

Research Pharmacist assigned to protocol:

[name]., R.Ph. [contact]

5.5 Subject Compliance Monitoring

Subjects will receive only one dose during the study. No additional medication adherence will be required.

5.6 Prior and Concomitant Therapy

Subjects will be required to discontinue therapy with anticholinergic, alpha-adrenergic antagonists, beta-adrenergic antagonists and other medications which could interfere with autonomic testing. Subjects may participate if the potentially interfering medication is held for five half-lives prior to the study. Enrolled subjects may not receive iron supplementation outside of study administration until after the Second Site Study Visit has been completed.

5.7 Packaging

The following is taken directly from the manufacture drug information:

Venofer® is supplied sterile in 10 mL, 5 mL, and 2.5 mL single-use vials. Each 10 mL vial contains 200 mg elemental iron, each 5 mL vial contains 100 mg elemental iron, and each 2.5 mL vial contains 50 mg elemental iron (20 mg/mL):

NDC-0517-2310-05 200 mg/10 mL Single-Use Vial Packages of 5

NDC-0517-2310-10 200 mg/10 mL Single-Use Vial Packages of 10

NDC-0517-2340-01 100 mg/5 mL Single-Use Vial Individually Boxed

NDC-0517-2340-10 100 mg/5 mL Single-Use Vial Packages of 10

NDC-0517-2340-25 100 mg/5 mL Single-Use Vial Packages of 25

NDC-0517-2325-10 50 mg/2.5 mL Single-Use Vial Packages of 10

NDC-0517-2325-25 50 mg/2.5 mL Single-Use Vial Packages of 25

5.8 Blinding of Study

This study will be double-blinded such that the subject and Primary Investigator will be blinded to the randomization of the subject.

5.9 Receiving, Storage, Dispensing and Return

5.9.1 Receipt of Drug Supplies

Venofer® is available in the United States market and is maintained as routine medication stock supply in the Mayo Clinic Hospital Pharmacy. The Clinic Research Pharmacy will obtain the drug used in this study from the stock supply in the Mayo Clinic Hospital Pharmacy.

5.9.2 Storage

All manufacture recommendations as listed in the drug monograph[28] will be followed:

- 1. Store in original carton at 20°C to 25°C (68° F to 77° F); excursions permitted to 15° to 30°C (59° to 86°F). [See USP Controlled Room Temperature].
- 2. Do not freeze.

3. *IV Admixture Stability:* Venofer®, when added to IV infusion bags (PVC or non-PVC) containing 0.9% NaCl at concentrations ranging from 1 mg to 2 mg of elemental iron per mL, has been found to be physically and chemically stable for 7 days at controlled room temperature (25°C ± 2°C).

- 4. Do not dilute to concentrations below 1 mg/mL.
- 5. Do not mix Venofer® with other medications or add to parenteral nutrition solutions for intravenous infusion.
- 6. Parenteral drug products should be inspected visually for particulate matter and discoloration prior to infusion.

5.9.3 Dispensing of Study Drug

Regular study drug reconciliation will be performed to document drug assigned, drug dispensed, drug returns, and drug remaining. This reconciliation will be logged on the drug reconciliation form, and signed and dated by the study team.

5.9.4 Return or Destruction of Study Drug

At the completion of the study, there will be a final reconciliation of drug dispensed, drug returns, and drug remaining. This reconciliation will be logged on the drug reconciliation form, signed and dated. Any discrepancies noted will be documented and investigated, prior to return or destruction of unused study drug. Drug destroyed on site will be documented in the study files.

6 Study Procedures

Assessment	Screening/Enrollment	Study Visit 1	Study Visit 2	Follow up by
	Visit (day -21 to day 0)	(day 0)	(day 7 ±2 days)	mail (6 months from day 0)
Informed consent/assent form	X			
Demographics	X			
Vital signs	X	X	X	
General physical exam	X			
Current medications	X	X	X	X
Inclusion/Exclusion Criteria	X	X	X	
Randomization	X			
Urine Beta-HCG for female subjects		X		
Questionnaires (COMPASS-31 and PedsQL)		X	X	X
IV/Venipuncture (CBC, ferritin, iron, TIBC, percent of iron saturation, upright and supine		X	X	

catecholamine)			
Tilt table test	X	X	
Orthostatic	X	X	
Symptom Scale			
(during tilt table)			
Intervention (study	X		
drug or placebo)			

6.1 Visit 1

- 1. Study visit ONE will be conducted in the Clinical Research Unit. All Study ONE visits will be scheduled such that the tilt table tests will be started during the window of 12 pm-4 pm. Study ONE visit will include:
 - a. Review of inclusion and exclusion criteria
 - b. Vital sign screen
 - c. For all female subjects:
 - i. Documentation of last menstrual period date
 - ii. Review of current birth control method and adherence
 - iii. Urine Beta-HCG obtained and documented as negative
 - d. Questionnaire completion
 - i. COMPASS-31 Instrument to assess autonomic symptoms [29]
 - ii. Pediatric Quality of Life Inventory (PedsQL) Version 4.0 [30]
 - e. IV/Venipuncture
 - i. Complete blood count
 - ii. Serum ferritin
 - iii. Total serum iron, total iron binding capacity and percent iron saturation
 - iv. Supine and standing catecholamine plasma levels
 - v. Estimated blood volume to be drawn is less than 15 mL
 - f. Ten minute, 70 degree head-up tilt table test which includes measurement of cardiovagal responses via heart rate variation to deep breathing (HRVDB), cardiac and vasomotor adrenergic responses via beat-to-beat heart rate, and blood pressure response with tilt and Valsalva maneuver.
 - g. Orthostatic symptom scale assessing orthostatic symptoms during tilt on a visual analog severity scale from 0-10
 - h. Administration of intervention (study drug OR placebo) followed by 10 mL NaCl 0.9% flush. Patients will have continuous cardiopulmonary monitoring (heart rate, respiratory rate and pulse ox) with blood pressure documented no less than every minutes during the infusion
 - i. Following the intervention, subjects will be monitored for signs and symptoms of intervention hypersensitivity for an additional thirty minutes. Patients will have continuous cardiopulmonary monitoring (heart rate, respiratory rate and pulse ox) with blood pressure documented no less than every fifteen minutes.
- 2. Time estimates for Study Visit One (4-4.5 hours)
 - a. Review of patient information (30 minutes)
 - b. Questionnaire completion (1 hour)
 - c. IV/Venipuncture (20 minutes)

- d. Tilt table test (1 hour)
- e. Intervention (1-1.5 hours)
- f. Subject observation (30 minutes)

6.2 Visit 2

- 3. Study visit TWO will take place 7 days ±2 days following study visit ONE. Study visit TWO will be completed in the Clinical Research Center. The visit will be scheduled such that the tilt table test will be started during the window of 12 pm-4pm. Study visit TWO will include:
 - a. Vital sign screen
 - b. Questionnaire completion
 - i. COMPASS-31 Instrument to assess autonomic symptoms
 - ii. Pediatric Quality of Life Inventory (PedsQL) Version 4.0
 - c. IV/Venipuncture
 - i. Complete blood count
 - ii. Serum ferritin
 - iii. Total serum iron, total iron binding capacity and percent iron saturation
 - iv. Supine and standing catecholamine plasma levels
 - v. Estimated blood volume to be drawn is less than 15 mL
 - d. Ten minute, 70 degree head-up tilt table test which includes measurement of cardiovagal responses via heart rate variation to deep breathing (HRVDB), cardiac and vasomotor adrenergic responses via beat-to-beat heart rate, and blood pressure response with tilt and Valsalva maneuver
 - e. Orthostatic symptom scale assessing orthostatic symptoms during tilt on a visual analog severity scale from 0-10
- 4. Time estimates for Study visit TWO (3-3.5 hours)
 - a. Review of patient information (30 minutes)
 - b. Questionnaire completion (1 hour)
 - c. IV/Venipuncture (20 minutes)
 - d. Tilt table test (1 hour)

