6.3 Mail follow-up

- 5. Follow up by MAIL will take place 6 months after study visit ONE and will include:
 - a. Questionnaire completion
 - i. COMPASS-31 Instrument to assess autonomic symptoms
 - ii. Pediatric Quality of Life Inventory (PedsQL) Version 4.0
 - b. Self-reported current medication list
 - c. Self-reported use of iron treatments (oral or intravenous) from study completion until 6 months post-study completion
 - d. Subjects will be provided a self-addressed, pre-paid envelope to return the materials to the primary investigator
- 6. Time estimate for Mail Follow-Up
 - a. Questionnaire completion (1 hour)

7 Statistical Plan

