7.1 Sample Size Determination

The two primary outcome variables in this study will be change in score on the COMPASS-31 survey and change in postural heart rate increase. For an anticipated change in the COMPASS-31 survey of 10 points, a sample size of 15 subjects per group (30 total) setting alpha at 0.05 and beta at 0.80 would be an adequate sample size to reject or accept the null hypothesis (power estimate >80%). For an anticipated change in postural tachycardia from 50 beats per minute to 30 beats per minute, a sample size of 15 subjects per group (30 total) setting alpha at 0.05 and beta at 0.80 would be adequate an adequate sample size to reject or accept the null hypothesis (power estimate >80%).

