7.2 Statistical Methods

Descriptive Statistics

Univariate descriptive statistics and frequency distributions will be calculated, as appropriate for all variables. Baseline values for demographic, clinical, and outcome variables (primary and secondary) will be tabulated for the treatment groups. These analyses will help identify potential confounding variables to be used as covariates in sensitivity analyses. Distributions across subgroups used in randomization will be compared to assess whether the randomization was successful in equalizing distributions of these prognostic variables across treatment groups. Putative prognostic variables that will be investigated through these descriptive analyses include subjective symptoms of autonomic dysfunction and cardiovascular indices.

Handling of Missing Data

Continuous data monitoring will be done by both study coordinator and the Primary Investigator using computer based systems. Scheduled review of study documentation by study coordinator and Primary Investigator will take place at a frequency of no less than every four to six weeks to assure that all reports are on file, accurate and complete. Prior to data analysis, trends and outliers will be reviewed to consider for potential missing data.

Primary Hypothesis: Treatment of iron deficiency with intravenous iron sucrose in an adolescent with Postural Orthostatic Tachycardia Syndrome will reduce their score on the COMPASS-31 survey by 10 points.

Data will be visually inspected for normality. Group comparisons will include Fisher's exact test for categorical variables and Wilcoxon rank sums for continuous variables. Confidence intervals will be calculated at 95%. All P-values will be 2-sided with values less than 0.05 considered significant. All analyses will be performed on an "intention to treat" basis

Secondary Hypothesis 1: Treatment of iron deficiency with intravenous iron sucrose in an adolescent with Postural Orthostatic Tachycardia Syndrome will reduce heart rate change during tilt table testing from 50 beats per minute to less than 30 beats per minute.

Data will be visually inspected for normality. Group comparisons will include Fisher's exact test for categorical variables and Wilcoxon rank sums for continuous variables. Confidence intervals will be calculated at 95%. All P-values will be 2-sided with values less than 0.05 considered significant. All analyses will be performed on an "intention to treat" basis

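### The day-7 COMPASS-31 has no off-site route, and section 4.4.2 does not commit to collecting it after withdrawal

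*Combined protocol and SAP*

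**What the plan says.** **The outcome.** Section 7.1: "The two primary outcome variables in this study will be change in score on the COMPASS-31 survey and change in postural heart rate increase". Section 7.2 makes a 10-point COMPASS-31 reduction the sole primary hypothesis. Neither section, nor 3.2, attaches a time point to the change.

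**When it is measured.** The section 6 schedule has COMPASS-31 at Visit 1, at Visit 2 (day 7 ±2) and by post at six months. For the second of these, section 6.2 says "Study visit TWO will be completed in the Clinical Research Center". The visit is put at 3 to 3.5 hours and also includes venipuncture, a Valsalva maneuver and a repeat 70-degree tilt. Sections 3.1, 6 and 6.2 give no postal, telephone or electronic alternative at day 7.

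**The same form off site.** Section 6.3 sends it at six months: "Subjects will be provided a self-addressed, pre-paid envelope to return the materials to the primary investigator". Section 3.1 says all subjects get this mailing.

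**After withdrawal.** Section 4.4.2 says that some later data may be worth collecting and that they bear on the soundness of the final analysis. Where consent is withdrawn, "for subject safety reasons, attempts will be made to obtain permission to collect follow up information whenever possible". It names no outcome. Section 4.4.1 allows, but does not require, replacement of withdrawn subjects.

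**Analysis.** Section 7.2: "All analyses will be performed on an 'intention to treat' basis". Its missing-data paragraph describes record review and gives no rule for an absent outcome. Section 7.3 defines only a protocol-compliant population.

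**The concern.** An intention-to-treat comparison needs an outcome from every randomised subject, or a stated way of dealing with those who have none. Here a patient-reported form that can be filled in anywhere shares the fate of a long clinic visit. If the subject does not come, the score that tests the primary hypothesis is gone, and the plan has neither a fallback for collecting it nor a method for analysing without it.

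Absence may also be related to the outcome. Section 8.1 lists fainting, lightheadedness, headache and nausea as risks of the tilt, and these overlap with the entry symptoms in section 4.1. How a subject feels in the week after infusion could plausibly affect whether they return. With 15 per arm, one or two forms are not negligible. Replacing a withdrawn subject restores the count but not the outcome of the person who was randomised.

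**Working it through.** **1. Can the day-7 score be obtained without Visit 2?** Setting 3.1, the section 6 schedule, 6.2, 6.3 and 4.4.2 side by side:

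- Attends and does everything: score obtained.
- Attends but declines tilt or blood draw: 6.2 lists the questionnaires before both and makes them conditional on neither, so the score can be obtained. The text does not say so outright.
- Does not attend, has not withdrawn: no route at day 7. The six-month form is still due, but the plan gives it no role in the primary analysis.
- Withdraws: collection is possible under 4.4.2 but not committed to.

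The gap is therefore non-attendance and withdrawal.

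**2. The plan's own figure.** Inputs: difference 10 points, 15 per group (section 7.1); 1:1 allocation (5.3); two-sided 0.05 (7.2: "All P-values will be 2-sided with values less than 0.05 considered significant"). Section 7.1 has "setting alpha at 0.05 and beta at 0.80"; I read this as power 0.80, since the same sentence claims power above 80%. No SD is given, so 15 per group cannot be reproduced. The largest SD that gives 80% power can be found instead.

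- Normal approximation: SD = 10 / [(1.960 + 0.842) × √(2/15)] = 10 / 1.023 = 9.78.
- Noncentral t, 28 degrees of freedom: SD = 9.44, a standardised difference of 10/9.44 = 1.060.
- For the planned Wilcoxon test, taking its efficiency relative to t as 0.955: about 9.20.

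**3. Power if Visit 2 scores are lost.** Two-sample t-test, noncentrality = (10/SD) × √[n₁n₂/(n₁+n₂)]. At SD 9.44 with 13+13 this is 1.060 × √6.5 = 2.70; with 12+12 it is 1.060 × √6 = 2.60.

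| Assumed SD | 15+15 | 13+13 | 12+12 |
|---|---|---|---|
| 8 | 91.0% | 86.4% | 83.3% |
| 9 | 83.6% | 77.6% | 73.9% |
| 9.44 | 80.0% | 73.7% | 69.9% |
| 12 | 59.6% | 53.2% | 49.7% |

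At SD 9.44, a loss of one score per arm gives 77.0%, and 14+13 gives 75.3%. If the claim of more than 80% is right, the SD is below 9.44 and the rows for 8 and 9 are the relevant kind. The SD 12 row applies only if that claim is wrong.

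**4. Bias.** If m of 15 in one arm are absent and their mean change differs from that of the observed subjects by k points, the observed mean is off by (m/15) × k. Over an assumed range of m = 1 to 3 and k = 5 to 10:

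- smallest: (1/15) × 5 = 0.33 points
- middle: (2/15) × 10 = 1.33 points
- largest: (3/15) × 10 = 2.0 points

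These compare with a 10-point target. The sign is that of k, which is unknown, and losses in the other arm may add to the shift or cancel it.

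**The case against.** Several points on the other side stand.

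- **Section 4.4.2 is not limited to safety.** A reader might infer from its last sentence that withdrawn subjects are followed for safety only. The section also appeals to the final analysis, and in that last sentence safety is the reason for asking, not a limit on what is collected. The fair criticism is that it is discretionary and names no outcome.
- **Refusing the tilt does not lose the form.** A reader might infer this from the bundled visit, but 6.2 sets no such condition. Nor does any section say that a form completed outside days 5 to 9 is discarded.
- **Day 7 is inferred.** The schedule makes it the evident primary time point, but no section states it.
- **Loss may be small.** There is one return visit about a week after a single infusion, every subject has already been through a qualifying tilt, and section 12.3 pays $100 for completion against $25 per on-site visit otherwise. No loss rate is given.
- **The direction of bias is not known.** A reader might suppose that subjects who did badly stay away, so that the iron effect is overstated. Improved subjects may also skip, and absence may be unrelated to symptoms.
- **On-site completion has merit.** It keeps place and mode the same as at baseline, and a home form recovers no tilt data.

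None of this supplies a route to the day-7 score for a subject who does not attend. The argument for a uniform setting is met by using the home form only as a fallback and testing its influence.

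**Conclusion.** The concern holds in a limited form. The day-7 COMPASS-31 can be obtained only by attending Visit 2, and its collection after withdrawal is not assured. A non-attender has no day-7 primary symptom score for the promised intention-to-treat analysis.

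The cost in power is modest and rests on assumptions: about 6 points for two lost scores per arm if the design sits exactly at 80% (80.0% to 73.7%), about 10 points for three (to 69.9%), and still above 80% in both cases if the SD is 8. Over the assumed range, one arm's mean shifts by 0.3 to 2.0 points in an unknown direction. The calculations use a t-test in place of the planned rank test, an SD that the protocol does not give, and loss counts chosen for illustration. The documents do not show that losses will occur at these rates or that they will favour iron. This is a cheap improvement rather than a flaw that invalidates the design.

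**What to change.** In section 6.2, state that COMPASS-31 and PedsQL are completed at Visit 2 whether or not the tilt or venipuncture is done.

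In sections 6.2 and 4.4.2, add text to this effect: *At Visit 1 each subject receives a day-7 COMPASS-31 and PedsQL with a prepaid envelope. A subject who cannot attend Visit 2, or who stops participation but agrees to this, completes both at home on days 5 to 9 and returns them.*

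In section 7.2, state that these scores enter the intention-to-treat analysis and that a sensitivity analysis omits scores not taken on site.

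Cost: two printed forms and an envelope for each of 30 subjects, short additions to three sections, and one further sensitivity analysis, with no new visit, procedure or staff. Downside: a few scores are completed at home rather than on site, and tilt data for absent subjects are not recovered. The change reduces missing scores. It does not replace the rule for a missing outcome that section 7.2 lacks.

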6.3 Mail follow-up

- 5. Follow up by MAIL will take place 6 months after study visit ONE and will include:
 - a. Questionnaire completion
 - i. COMPASS-31 Instrument to assess autonomic symptoms
 - ii. Pediatric Quality of Life Inventory (PedsQL) Version 4.0
 - b. Self-reported current medication list
 - c. Self-reported use of iron treatments (oral or intravenous) from study completion until 6 months post-study completion
 - d. Subjects will be provided a self-addressed, pre-paid envelope to return the materials to the primary investigator
- 6. Time estimate for Mail Follow-Up
 - a. Questionnaire completion (1 hour)

7 Statistical Plan

7.1 Sample Size Determination

The two primary outcome variables in this study will be change in score on the COMPASS-31 survey and change in postural heart rate increase. For an anticipated change in the COMPASS-31 survey of 10 points, a sample size of 15 subjects per group (30 total) setting alpha at 0.05 and beta at 0.80 would be an adequate sample size to reject or accept the null hypothesis (power estimate >80%). For an anticipated change in postural tachycardia from 50 beats per minute to 30 beats per minute, a sample size of 15 subjects per group (30 total) setting alpha at 0.05 and beta at 0.80 would be adequate an adequate sample size to reject or accept the null hypothesis (power estimate >80%).

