3.2 Primary Study Endpoints

The primary endpoint for this study is to determine the effects of iron sucrose on 1) self-reported symptoms of autonomic dysfunction assessed by a validated questionnaire and 2) cardiovascular indices measured by tilt table testing.

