4.1 Inclusion Criteria

• Adolescent patients (age 12 to 21 years) with chronic (>3 months) symptoms of orthostatic intolerance, including but not limited to lightheadedness, syncope, headache, fatigue, weakness, sweating, nausea and heart palpitations.

• Symptomatic orthostatic heart rate increment ≥40 bpm during a 10 minute 70 degree head up tilt study

- Presence of non-anemic iron deficiency, defined as serum ferritin levels <20 ug/L with hemoglobin no less than 1 gm/dL below the normal reference range as defined for age and gender
- Consent obtained from responsible guardian AND from subjects, 12-17 years of age
- Consent obtained for subjects 18 years of age and older

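### The heart-rate comparison uses the Visit 1 tilt only by subtraction; prespecifying adjustment for it would usually gain precision, by an amount the plan's figures cannot fix

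*Combined protocol and SAP*

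**What the plan says.** Section 7.1 defines the outcomes: "The two primary outcome variables in this study will be change in score on the COMPASS-31 survey and change in postural heart rate increase". It anticipates a fall from 50 to 30 bpm, with 15 subjects per group and alpha 0.05, and claims power above 80%. It gives no SD, no correlation between visits and no expected change on placebo.

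Section 7.2 gives the same test paragraph under each hypothesis: "Group comparisons will include Fisher's exact test for categorical variables and Wilcoxon rank sums for continuous variables". No covariate is named for that test. That the rank-sum test is run on the change follows from reading 7.1 and 7.2 together; neither section says it in one place.

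Covariates do appear in 7.2, under descriptive statistics. Of the baseline tabulations it says: "These analyses will help identify potential confounding variables to be used as covariates in sensitivity analyses". The candidate prognostic variables "include subjective symptoms of autonomic dysfunction and cardiovascular indices". No model is given.

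Section 6 schedules a tilt test before dosing at Visit 1 and again at Visit 2, so the baseline increase is collected for everyone. Section 4.1 selects on the same variable: "Symptomatic orthostatic heart rate increment ≥40 bpm during a 10 minute 70 degree head up tilt study".

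The status of the endpoint differs between sections. Section 3.2 includes "cardiovascular indices measured by tilt table testing" in the primary endpoint and 7.1 agrees, while 7.2 introduces the same question as "Secondary Hypothesis 1: Treatment of iron deficiency with intravenous iron sucrose in an adolescent with Postural Orthostatic Tachycardia Syndrome will reduce heart rate change".

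**The concern.** A raw change score fixes the slope of Visit 2 on Visit 1 at 1. A postural increase is already a difference of two heart rates, so its change between visits is a difference of differences and carries the measurement noise of both tilts. If the within-arm slope is well below 1, subtracting the whole Visit 1 value brings in noise that an estimated slope would leave out. With equal variances and rho at or below 0.5, the change is no less variable than the Visit 2 value alone.

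With 15 per arm, two things are at stake. One is the width of the interval for the 20 bpm effect. The other is sensitivity to a chance difference between arms at Visit 1. Choosing covariates after seeing the baseline tables also leaves the adjusted result open to selection, where naming one covariate in advance would not.

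**Working it through.** **Inputs from the documents.** Difference 50 - 30 = 20 bpm (7.1, taking no change on placebo); 15 per arm (7.1); two-sided 0.05 (7.2). **Assumed, because not given:** the SD of change, rho, approximate normality and, unless noted, equal variance s² at the two visits.

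**The plan's own power.** It cannot be reproduced without an SD, so I solve backwards. Power of exactly 80% requires:
- normal approximation: SD of change = 20 / [(1.960 + 0.842) × √(2/15)] = 19.55 bpm
- t-test: standardized difference 1.060, so SD = 20 / 1.060 = 18.87 bpm
- rank-sum: 18.87 × √(3/π) = about 18.4 bpm

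With SDs of 15, 18, 20 and 25 bpm the normal-approximation power is 95.5%, 86.1%, 78.2% and 59.1%. The claim of more than 80% therefore holds only if the SD of change is below about 18 to 20 bpm.

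**Precision.** Var(change) = 2s²(1 - rho). Var(adjusted) = s²(1 - rho²). The ratio is (1 + rho)/2, which is below 1 for any rho below 1.

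**Power after adjustment, starting from about 80% on raw change.** The t column uses 27 df and allows for estimating the slope. The last column compares rank-sum on change with rank-sum on residuals from the regression on Visit 1, at an SD of change of 18.

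| rho | variance ratio | normal approx. | t, 27 df | simulated, rank tests |
|---|---|---|---|---|
| 0.3 | 0.65 | 93.5% | 92.6% | 80.7 to 92.7% |
| 0.5 | 0.75 | 89.9% | 88.7% | 81.1 to 89.1% |
| 0.7 | 0.85 | 86.0% | 84.6% | 81.5 to 85.7% |
| 0.8 | 0.90 | 84.0% | 82.5% | 79.9 to 82.5% |
| 0.9 | 0.95 | 82.0% | 80.4% | no gain |

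A second simulation put the rank-test gains at about 13, 8, 5 and 1 points for rho 0.3, 0.5, 0.7 and 0.8. Going straight from rank-sum on change to ANCOVA gave 80.2 to 94.4%, 80.3 to 91.0%, 80.3 to 88.1% and 80.1 to 85.4% at the same values. About 3 of those points come from leaving the rank test under normal data, and I do not credit them to adjustment. Type I error of the residual rank-sum test was 4 to 5%.

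**Dependence on the starting power.** At rho 0.5 (normal approximation) the gain is 9.9 points from 80%, 6.3 from 90% and 3.6 from 95%.

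**A smaller SD.** Take an assumed between-subject SD of 12, within-subject SD of 10 and population mean of 45 bpm. The SD of change is 10 × √2 = 14.1 bpm. With selection at 40 bpm or more on an earlier tilt, rho falls from 0.59 to 0.49. Rank-sum power on change is then already about 94 to 95% and rises to about 98%.

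**Visit 1 as the qualifying tilt.** The visit variances are then unequal and (1 + rho)/2 does not apply. With the same components, 97% becomes about 97.5%. Rescaled to 80% power with the cut at the population mean, moving to ANCOVA gains about 6, 5 and 3 points at unrestricted rho 0.5, 0.6 and 0.8. Less the 3 points for leaving the rank test, that is about 3, 2 and 0.

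**Chance imbalance.** Given an observed Visit 1 difference D between arms, the change-score estimate departs from the adjusted one by (1 - slope) × D in size. For example, at rho 0.5 and a single-visit SD of 18.9, D has SD 18.9 × √(2/15) = 6.9 bpm, so a one-SD imbalance shifts the estimate by 0.5 × 6.9 = 3.5 bpm.

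**The case against.** The strongest reply is that the planned test is valid and the benefit is of unknown size. Much of this stands.

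- A reader might infer that adjustment is worth 8 to 10 points outright. That holds near rho 0.5 with power close to 80%, and the documents give neither condition: section 7.1 states a lower bound on power, not a value.
- A reader might argue that the 40 bpm entry rule forces rho down and so makes the gain large. The variance components that bring rho to 0.49 also imply an SD of change of 14.1 bpm, where power is already high. It is also unsettled which tilt qualifies a subject. The section 6 schedule shows tilts only at Visits 1 and 2, the screening list in 4.3 names none, and eligibility is reviewed again at Visit 1. Randomization at screening points to an earlier tilt but does not establish one. If Visit 1 qualifies subjects, a mean of 50 with a floor of 40 implies an SD below 10 under a truncated normal. That is hard to square with a single-visit SD of 18.9, which is what an SD of change of 18.9 requires at rho 0.5.
- A reader might infer that the change score is biased. Under randomization it is not; the shift above is conditional on an observed imbalance.
- A reader might say that the plan ignores baseline. It does not: 7.2 tabulates it, lists cardiovascular indices as candidates and allows covariates in sensitivity analyses.

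The objection does not remove the main point. The adjustment uses data already collected, rarely costs power, and is better fixed in advance than chosen from baseline tables.

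**Conclusion.** The point holds as one about efficiency and prespecification. The main heart-rate analysis, as read from 7.1 and 7.2, uses the Visit 1 tilt only by subtraction, and a prespecified adjustment would generally be more precise.

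Its size rests on an assumed SD and rho. At about 80% power on raw change, the gain from adjustment is roughly 12 to 13 points at rho 0.3, 8 to 10 at 0.5, 4 to 6 at 0.7 and 1 to 4 at 0.8. It is about 0 to 4 points if the SD of change is nearer 14 bpm or if Visit 1 is the qualifying tilt. The documents do not show which case applies. They do not support calling the planned test invalid or the trial underpowered on this ground.

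Sections 3.2 and 7.1 treat heart rate as primary and 7.2 as secondary. The adjustment helps under either label, but the label must be settled.

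**What to change.** In 7.2, name one main heart-rate analysis: ANCOVA of the Visit 2 postural increase on treatment, with the Visit 1 postural increase as the single covariate. Take the estimate, the 95% confidence interval and the p-value from that same model. Pairing a rank-based p-value with an ANCOVA interval could produce results that disagree. Keep the rank-sum test on change, or on residuals, as a sensitivity analysis.

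Reconcile 3.2 and 7.1 with 7.2 on whether heart rate is primary or secondary. State in 7.1 the SD of change and the correlation assumed, so that the power claim can be checked, and say which tilt establishes eligibility.

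The cost is a few sentences and a few lines of code, with no new data. The statistical price is one degree of freedom and a linearity assumption; the retained rank-sum analysis guards against marked non-normality.
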